Participants were nurses recruited through purposive sampling in 2025. A power analysis was conducted to determine the required sample size for the intervention and control groups. Based on a previous study examining the effect of Balint group training on burnout (Huang et al., 2020), the minimum required sample size was calculated as 28 participants, with an alpha (α) level of 0.05, an effect size (d) of 1.70, and a power of 99%. Considering the nurses' shift schedules, potential attrition was anticipated.

All nurses working in hospitals across various cities nationwide where the study was conducted were invited to participate through announcements posted on social media platforms. The inclusion criteria were: (i) having worked as a nurse in the same clinical setting for at least one year and (ii) providing informed consent to participate. The exclusion criterion was the presence of a communication impairment that could hinder participation (e.g., hearing or speech disorder). The criteria for discontinuation from the study included: (1) voluntary withdrawal, (2) missing at least two sessions, and (3) incomplete or missing data on the study instruments.

A total of 50 nurses contacted the research team and underwent eligibility screening. Of these, 17 declined participation after learning that session attendance was mandatory, and three did

not meet the inclusion criteria. Ultimately, 30 nurses who met the inclusion criteria were enrolled in the study, taking anticipated attrition into account.

Randomization and prevention of bias

Participants were randomly assigned to either the intervention or control group at a 1:1 ratio using simple randomization. An independent academic not involved in the study generated a random number list via a computer program to minimize selection bias. Eligible nurses were then sequentially allocated to the intervention ($n = 15$) and control ($n = 15$) groups according to the random sequence. Group assignments were determined using a lottery method conducted by two independent academics unaffiliated with the study. The letter “X” represented the intervention group, while “Y” represented the control group. Due to the nature of the Balint group intervention, blinding of participants and researchers was not feasible. Nevertheless, allocation concealment was maintained: data were coded (Group X/Group Y) and analyzed by an independent statistician blinded to group assignments to minimize bias.

Procedure

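### Does describing X/Y coding and a blinded statistician as allocation concealment show that assignment was open to selection bias?

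*Combined protocol and SAP*

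**What the plan says.** Everything on allocation stands in the section on randomization and prevention of bias. It names the method: "Participants were randomly assigned to either the intervention or control group at a 1:1 ratio using simple randomization". It names the source of the sequence: "An independent academic not involved in the study generated a random number list via a computer program to minimize selection bias". It then reports the allocation ("Eligible nurses were then sequentially allocated to the intervention" and control groups, 15 in each, following the sequence) and adds a second device: "Group assignments were determined using a lottery method conducted by two independent academics unaffiliated with the study". Of the two code letters, X "represented the intervention group, while" the other, Y, stood for control. The section concedes that "blinding of participants and researchers was not feasible", and then offers the reassurance at issue: "Nevertheless, allocation concealment was maintained: data were coded (Group X/Group Y) and analyzed by an independent statistician blinded to group assignments".

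The paragraphs just before it, under Methods, give the flow into the trial. They begin "A total of 50 nurses contacted the research team and underwent eligibility screening" and report 17 refusals, three ineligible nurses and 30 enrolled. Informed consent is one of the two inclusion criteria, and Ethical considerations says that all participants gave it. Procedure gives times for the post-test and both follow-ups but not for the pre-test. The Control group section says that both arms completed the instruments at the same times.

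**The concern.** Allocation concealment means that whoever admits a participant cannot know or guess the arm that participant will enter. Coded data and a blinded analyst belong to a later stage and cannot provide this, so the document claims one safeguard and describes another.

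Four further gaps add to the doubt:

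- The list and the lottery are each said to have decided the groups.
- Simple randomization does not guarantee equal arms, yet exactly 15/15 is reported with no restriction described.
- The meaning of X and Y is printed in the document, so the code would not blind a statistician who had read it.
- Nothing places the pre-test before assignment was known.

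The trial is open, both outcomes are self-reported, and the research team handled first contact. If that team could see the next assignment, it could have steered nurses between arms. If nurses answered the pre-test already knowing their arm, the baseline could be shaded, and with it the group-by-time comparison.

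**Working it through.** **Flow into the trial (Methods).** 50 screened − 17 declined − 3 ineligible = 30 enrolled, which matches the reported 30 and the 15 + 15 allocated. The 17 refusals are attributed to mandatory attendance and come before enrolment in the account, so they are not evidence of withdrawal after an unwelcome assignment.

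**Order of consent and allocation.** Consent is an inclusion criterion, those enrolled met the criteria, and eligible nurses were then allocated. Consent therefore precedes allocation. Only the place of the pre-test is unstated.

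**Does 15/15 contradict simple randomization?** With 30 independent 1:1 assignments,

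P(15/15) = C(30,15) / 2^30 = 155,117,520 / 1,073,741,824 = 0.144.

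This is about one draw in seven, and it is the single most likely split. It neither proves nor excludes a forced balance.

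**Do the list and the lottery conflict?** They can be read as two steps: the list sorts the nurses into two sets, and the lottery decides which set receives the intervention. The text does not say this, but nothing in it rules it out. On either reading, people outside the study carried out the step.

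**How predictable could assignments have been?** This depends on conditions that the document does not state:

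| Condition (assumed) | Expected correct guesses out of 30 |
|---|---|
| Simple randomization, list hidden | 30 × 0.5 = 15.0 (50%) |
| 15/15 forced, list hidden, earlier assignments known | 18.0 (59.9%) |
| List visible to the enroller | 30 (100%) |
| All 30 enrolled before any allocation | not applicable: no enrolment decision remains |

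The second row assumes the enroller always guesses the arm with more places left. With a and b places remaining, the expected number correct is f(a,b) = max(a,b)/(a+b) + [a/(a+b)] f(a−1,b) + [b/(a+b)] f(a,b−1), with f(0,0) = 0 and a term dropped once its arm is full. This gives f(15,15) = 17.96, and 17.96 / 30 = 59.9%.

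Rows two and three require nurses to be still entering while assignments are being revealed, or an exposed list. The document describes neither. Its order (screened, enrolled, then allocated) and the closed intervention group fit the last row at least as well, although the word for sequential allocation leaves one-at-a-time assignment possible. The table shows how much depends on an unreported step. It does not estimate bias in this trial.

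**What could still be altered?** The 15/15 allocation is reported as completed. Outcome measures gives Cronbach's alpha for all four assessments, including the second follow-up, so the data had been collected. Statistical analysis is written in the past tense. One sentence in Procedure is in the future tense, but it cannot outweigh reliability figures already computed from the last visit.

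**The case for a change.** The strongest case for a change is that this is more than a missing detail. A named safeguard is asserted, and the evidence given for it is of another kind. Independent generation of a list is not the same as hiding it. Researchers were not blinded, and in an open trial with self-reported outcomes a reader is entitled to know whether selection was possible. If all 30 nurses were enrolled first, one sentence would settle the matter in the trial's favour, at almost no cost.

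Much of this stands. The label is wrong, the holder of the list and the role of the lottery are undescribed, the pre-test is not timed against assignment, and nothing says that the X/Y key was kept from the statistician.

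The inference to a flawed design does not stand. The researchers' lack of blinding is attributed to the nature of the intervention, which says nothing about knowledge of upcoming assignments. Nothing shows that the statistician used the key. Concealment would not have protected self-reported follow-up scores in an open trial in any case, and a pre-test before assignment protects only the baseline report. Holding the list back or relabelling the arms comes too late for allocation and, on the document's own account, for the analysis.

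**Conclusion.** The point is a mislabelled safeguard and a thin description of allocation, and it calls for no change to the plan. The X/Y coding is analyst blinding. Concealment of upcoming assignments is undemonstrated, which is different from shown to have failed, and a careful reader should take it that way. Independent academics handling both the list and the lottery are a partial safeguard. The 15/15 split is compatible with the stated method (probability 0.144).

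The size of any selection bias cannot be derived from the documents. For enrolment decisions it would be nil if all 30 nurses were enrolled before allocation, a reading that the text allows but does not confirm. Clearer wording would help a reader judge the trial, but it would correct no figure, alter no analysis rule and change no result. This conclusion assumes that the past-tense account of allocation, data collection and analysis is accurate.

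### Does describing coded, analyst-blinded data as allocation concealment, with the codes X and Y defined in the same paragraph, weaken the trial's protection against bias?

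*Combined protocol and SAP*

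**What the plan says.** The section on randomization and prevention of bias sets out the allocation in a few sentences. Nurses were assigned "at a 1:1 ratio using simple randomization". An independent academic "generated a random number list via a computer program to minimize selection bias", and eligible nurses were allocated in order from that sequence, 15 to each arm. The text then adds: "Group assignments were determined using a lottery method conducted by two independent academics unaffiliated with the study". It also fixes the lettering, with X for the intervention arm and Y for the control arm.

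The section next accepts that "blinding of participants and researchers was not feasible", and continues: "Nevertheless, allocation concealment was maintained: data were coded (Group X/Group Y) and analyzed by an independent statistician blinded to group assignments".

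Other sections bear on the point:

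- **Methods:** of 50 nurses screened, 17 declined and three were ineligible, and "30 nurses who met the inclusion criteria were enrolled in the study". Informed consent is an inclusion criterion. Grounds for discontinuation include "missing at least two sessions" and incomplete instrument data.
- **Outcome measures:** both scales are self-reported, and study-specific Cronbach's alphas are given for all four assessments.
- **Statistical analysis:** the data are screened for missing values and checked for normality, and then a two-way mixed ANOVA is run.

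**The concern.** Allocation concealment means that whoever enrols a participant cannot foresee the next assignment. Analyst blinding means that whoever handles the finished data does not know which arm is which. The sentence claims the first and supports it only with the second. A reader could credit the trial with a safeguard that this sentence does not describe.

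The analyst blinding also looks fragile. The dataset labels are the same letters that the paragraph defines as intervention and control, and no section says who held the key. Participants and researchers were unblinded and the outcomes are self-reported, so the statistician is the only party described as blinded. Some steps before the tests call for judgement, and with 15 nurses per arm a single choice could be noticeable. If the statistician could read the codes, those choices would be exposed to knowledge of the arms.

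Two smaller doubts go with this. The text does not say how the random list and the lottery fit together. An exact 15:15 split is also not guaranteed by simple randomization.

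**Working it through.** The plan's only design calculation is the minimum sample of 28 (alpha 0.05, d = 1.70, power 99%). It reproduces with a two-sided two-sample t-test: 14 per arm gives power 0.991, and 13 per arm gives 0.986. It has no bearing on concealment or blinding, so most of the check is a reading of the text.

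**1. Was concealment at enrolment compromised?** The counts in Methods close: 17 + 3 + 30 = 50. On the natural reading, screening and enrolment of all 30 nurses came before allocation, and consent was a condition of entry. People outside the study generated the list and ran the lottery. Nothing shows that anyone enrolling nurses could see a coming assignment. The text does not name who held the list or when assignments were released. That is missing detail, not evidence of failure.

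**2. Do the list and the lottery conflict?** Not necessarily. An ordinary reading is that the list formed two sets of nurses and the lottery decided which set was X and which was Y.

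**3. Is 15:15 a warning sign?** Under simple randomization of 30, the probability of an exact split is C(30,15)/2^30 = 155,117,520/1,073,741,824 = 0.144. That is an unremarkable result. If the split was fixed in advance, equal arms do no harm to the comparison.

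**4. Was the analyst blinding broken?** Decoding X and Y requires the statistician to have had this paragraph, or the key, before or during the analysis. Two pieces of text bear on that:

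- The section says the statistician was independent and blinded to group assignments.
- Apart from one future-tense sentence opening Procedure, the account is mostly in the past tense, and Outcome measures already reports alphas for all four assessments. The text therefore reads as written after data collection. Stating afterwards what X and Y meant does not show that the analyst knew at the time.

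**5. How large could one analyst decision be?** Assume, beyond what the plan says, that the statistician drops one of 15 nurses lying k SD from the arm mean. That mean then moves by k/14 SD:

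- k = 1: 1/14 = 0.071 SD
- k = 2: 2/14 = 0.143 SD

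The standard error of a single-time difference at 15:15 is sqrt(2/15) = 0.365 SD. The shifts are 0.071/0.365 = 20% and 0.143/0.365 = 39% of it. Against the planning effect they are 0.071/1.70 = 4% and 0.143/1.70 = 8%.

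This only shows scale. The plan has no step that excludes outlying scores: it screens for missing values and assesses normality, and its data-related ground for discontinuation is incompleteness. The yardstick is also a single-time standard error, whereas the planned model is a mixed ANOVA over repeated assessments.

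**6. Would new labels help?** With the key withheld, X/Y and A/B protect equally. With the key known, neither protects. The gain from relabelling is zero unless the key was actually disclosed, which the document does not suggest. If the analysis has already been run, as the reported alphas suggest, relabelling would be too late anyway.

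**The case for a change.** The best case for acting is that the only blinding claim in an otherwise open trial carries the wrong name, and that its code is printed in the combined protocol and SAP, the very document an analyst would be expected to use. The usual reply that every coded analysis has a key is weaker when the key sits beside the code. A correction would cost about one paragraph. Session attendance, or discontinuation for missed sessions, would also reveal the intervention arm under any labels, because controls had no sessions. Finally, no section says whether the pre-test was completed before nurses learned their arm, and a self-reported baseline could be affected by that knowledge.

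Part of this stands. The term is wrong, and the document does not say who held the list or the key, or when assignments were released. A trial report should be clear on these.

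The rest does not carry the point further. That the statistician worked from this text is an assumption, and it runs against the stated blinding. No section says that attendance or discontinuation reasons were in the analyst's file. The timing of the pre-test concerns baseline reporting, whereas concealment protects the enrolment decision, so it is not a condition for claiming concealment.

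**Conclusion.** No change to the plan follows. The sentence puts the name of one safeguard on another, and the section leaves out custody details that those running the trial would know. That is a slip of terminology with a gap in reporting. It is not a flaw in the design or the analysis.

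If the plan is followed as written, with an independent list, an independent lottery, a blinded statistician and a specified mixed ANOVA, then correcting the term or swapping the letters alters no allocation, data value or test. The effect on the results is zero. The shift of 0.07 to 0.14 SD depends on an exclusion step that the plan does not contain, so it should not be read as an estimate of bias.

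This conclusion rests on two assumptions: that the statement that the statistician was blinded is true, meaning the X/Y key was not available during the analysis, and that enrolment preceded allocation, as the participant counts indicate. The document supports both and contradicts neither. Evidence that the statistician held the key would reopen the question of how the analyst blinding is described. It would not by itself show bias.

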In Balint groups, nurses explore strategies to better manage challenging patient-nurse relationships and enhance their interpersonal skills (Huang et al., 2020). These groups are particularly effective in raising awareness of the emotions and thoughts associated with patients perceived as "difficult" (Yousefzadeh et al., 2024). Balint-based interventions also provide social support by creating a relatively safe environment while respecting nurses' professional experiences (Lv, 2023). Moreover, considering nurses' working conditions, Balint-based interventions are regarded as easily implementable, time-efficient, and evidence-based approaches (Yang et al., 2021).

Rationale

Previous studies have primarily examined the effectiveness of Balint therapy among residents and medical students (Huang et al., 2020a; McCarron et al., 2024). In recent years, there has been growing interest in implementing Balint groups with nurses (Lu et al., 2020). Existing literature indicates that Balint therapy is effective in reducing burnout and enhancing self-efficacy (Shan et al., 2024), improving communication skills (Yang et al., 2021), and promoting quality of work-life among nurses (Huang et al., 2020). However, further research is needed to examine the long-term effects and sustainability of this intervention among nurses. To the best of our knowledge, this study represents the first application of a Balint-based intervention with nurses in the country, highlighting a gap in the literature regarding its effectiveness. Given the demanding working conditions of nurses, a Balint-based group intervention may provide meaningful support for their psychosocial well-being and facilitate positive patient care outcomes.

The current study aims to measure the effect of a Balint-based group intervention on burnout and communication skills in nurses. The research hypotheses are as follows:

H0-1: There is no significant difference in burnout levels between the intervention and control groups.

H0-2: There is no significant difference in communication skills between the intervention and control groups.

Study design

The study used a two-arm parallel-group randomized controlled design with pre-test and post-test measurements and follow-up assessments at one and three months.

Methods

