The Participant Information Form was prepared by the researchers based on literature (Huang et al., 2020; Elzain et al., 2023). This form consists of seven questions to determine participants age, gender, educational status, marital status, physical and mental health status, years of employment.

Primary Outcome Measure: The Maslach Burnout Inventory (MBI) was developed by Maslach and Jackson (1981), and its Turkish validity and reliability were established by Ergin (1992). The MBI is a self-report instrument used to assess burnout levels and consists of 22 items across

three subscales: Emotional Exhaustion, Depersonalization, and Personal Accomplishment. Each item is rated on a 0–4 scale. Higher scores on the Emotional Exhaustion and Depersonalization subscales indicate greater burnout, whereas higher scores on the Personal Accomplishment subscale indicate lower burnout. In this study, the Personal Accomplishment subscale was reverse-coded so that all subscales aligned in the same direction, with higher total scores reflecting higher levels of burnout. Ergin (1992) reported Cronbach's alpha (α) coefficients for the Emotional Exhaustion, Depersonalization, and Personal Accomplishment subscales as .83, .65, and .72, respectively. In the present study, Cronbach's alpha coefficients for the pre-test, post-test, first follow-up, and second follow-up assessments were .85, .89, .87, and .88, respectively.

Secondary Outcome Measures: The Communication Skills Scale for Health Professionals (CSSHP) was developed by Leal-Costa et al. (2016), and its Turkish validity and reliability were established by Mendi et al. (2020). The scale is a self-report instrument designed to assess the communication skills of health professionals. It comprises 18 items across four subscales, with each item rated on a 1–6 Likert scale. Higher scores indicate better communication skills. Mendi et al. (2020) reported Cronbach's alpha (α) values for the subscales ranging from .72 to .79. In the present study, Cronbach's alpha coefficients for the pre-test, post-test, first follow-up, and second follow-up assessments were .89, .88, .92, and .92, respectively.

Statistical analysis

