Data analysis was conducted using IBM SPSS Statistics for Windows, version 26.0 (IBM Corp., Armonk, NY, USA). The dataset was screened for missing values and assessed for normality assumptions prior to analysis. Differences between the intervention and control groups were examined using Pearson's chi-square test for categorical variables and the independent samples t-test for continuous variables. Fisher's exact test was applied when the expected cell count was less than five. A two-way mixed ANOVA was performed to evaluate between-group, within-time, and group \times time interaction effects. Bonferroni correction was applied for multiple comparisons. Effect sizes were reported using Cohen's d for within-group comparisons and partial eta squared (η^2) for the mixed ANOVA. The interpretation of partial eta squared values followed the classifications proposed by Cohen (1992): $\eta^2 \geq .01$ was considered small, $\eta^2 \geq .06$ moderate, and $\eta^2 \geq .14$ large. Statistical significance was set at $p < .05$.

Ethical considerations

Ethical approval for this study was obtained from the Bilecik Seyh Edebali University Non-Interventional Clinical Research Ethics Committee (19.09.2024 – 280361). Prior to participation, nurses were provided with detailed information about the purpose of the study, the procedures to be performed, and the voluntary nature of participation. Informed consent was obtained electronically from all participants via an online consent form. Participants were assured of confidentiality, the right to withdraw from the study at any time, and that their personal information would not be shared.

References

Cohen, J. (1992). Statistical power analysis. *Current Directions in Psychological Science*, 1(3), 98–101. <https://doi.org/10.1111/1467-8721.ep10768783>

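### The analysis plan lists no between-group difference adjusted for the pre-test and no confidence interval, although the aim is to measure the effect and the pre-test is collected

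*Combined protocol and SAP*

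**What the plan says.** The Rationale gives the aim: "The current study aims to measure the effect of a Balint-based group intervention on burnout and communication skills in nurses". The hypotheses are "H0-1: There is no significant difference in burnout levels between the intervention and control groups" and "H0-2: There is no significant difference in communication skills between the intervention and control groups". Neither names an assessment or a model term. Study design provides for "pre-test and post-test measurements and follow-up assessments at one and three months", so each scale is measured four times, once before the intervention. Outcome measures makes the MBI primary and the CSSHP secondary, and gives no time point for either.

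Under Statistical analysis, "A two-way mixed ANOVA was performed to evaluate between-group, within-time, and group" by time interaction effects. The same section lists:
- an independent-samples t-test for continuous variables, without saying which variables or which assessments;
- a Bonferroni correction, without saying which comparisons it covers;
- two effect sizes: Cohen's d, for within-group comparisons only, and partial eta squared.

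Neither a pre-test-adjusted group difference nor a confidence interval appears anywhere in the document.

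**The concern.** A reader of this trial will want to know how much lower burnout was in the intervention arm than in the control arm, at what time, and how precisely that is known. None of the listed summaries is set up to answer this. Within-group d describes change inside one arm; it is not a treatment effect, because it includes whatever change would have occurred without the intervention. Partial eta squared has no direction and no units. The t-test, if it is meant for outcomes at all, ignores the pre-test.

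The plan also leaves open which of the three ANOVA effects bears on H0-1 and H0-2. The natural reading, not stated, is that the pre-test is one of four levels of time. If so, and if the group main effect were read as the test of H0-1, that effect would average in an assessment made before any intervention. It would then understate a real post-intervention difference and carry part of any chance imbalance at pre-test.

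**Working it through.** **Inputs from the document.** 15 per arm (Randomization and prevention of bias); four assessments, one before the intervention (Study design); d = 1.70, alpha 0.05, power 99%, 28 participants (Methods).

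**Assumptions not in the document.** Equal correlation rho between assessments, 0.3 to 0.8; equal SDs; complete data on all 30; a two-sided test; any effect other than a constant 1.70.

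**1. The plan's own figure.** For a two-sided two-sample t-test with m per arm, the noncentrality is 1.70 × √(m/2) on 2m − 2 df. With m = 13 power is 98.6%; with m = 14 it is 99.1%. So 28 in total reproduces.

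**2. What the group main effect would estimate.** With four levels of time and a constant difference d after the intervention, it estimates (0 + d + d + d)/4 = 0.75d. At d = 1.70 that is 1.275. It also carries one quarter of any chance difference at pre-test.

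**3. Do the group and group by time tests disagree at the plan's effect?**
- Group: t on 28 df, effect 0.75d, variance (2/15)(1 + 3rho)/4.
- Group by time: F(3, 84), with lambda = (15/2) × Σ(δt − mean)²/(1 − rho). For a constant effect the sum is (0.75d)² + 3(0.25d)² = 0.75d², which is 2.1675 at d = 1.70.
- At rho = 0.5 the group variance is 0.0833 and power is 98.9%. Lambda is 7.5 × 2.1675/0.5 = 32.5 and power is 99.9%.
- Under equal correlation the two tests are independent, so they disagree with probability p1(1 − p2) + p2(1 − p1), here about 1.2%.

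At rho 0.3, 0.5, 0.7 and 0.8 disagreement is 1.6%, 1.2%, 3.1% and 4.5%.

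**4. What pre-test adjustment gains at one assessment.** Half-widths are in SD units.
- Unadjusted, known SD: 2.048 × √(2/15) = 0.748.
- Adjusted, before any imbalance penalty: 2.052 × √(2/15) × √(1 − rho²) = 0.749 × 0.954, 0.866 or 0.714 = 0.715, 0.649 or 0.535 at rho 0.3, 0.5 or 0.7.
- Two small corrections apply. The estimated SD averages about 1 − 1/(4 df) of the true SD, roughly 0.991 in both cases. Chance pre-test imbalance inflates the adjusted variance by about 1 + 1/26 on average, a factor of 1.019 on the half-width.
- Unadjusted: 0.748 × 0.991 = 0.74. Adjusted: the three values × 0.991 × 1.019 = about 0.72, 0.655 and 0.54.

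Simulated mean half-widths agree: about 0.74 unadjusted against 0.72, 0.66 and 0.54 adjusted. The reductions are about 3%, 11% and 27%.

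**5. A single deciding contrast is a trade-off.** At an assumed constant effect of 0.8 SD and rho 0.5, ANCOVA on the mean of the three post-baseline scores has about 90% power and group by time 58%. If 0.8 fades to 0.4 and then 0, the order reverses: 37% against 54%.

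**The case against.** The strongest reply is that the planned test is sound. Group by time uses the pre-test as a level of time, is valid given sphericity, and is followed by corrected comparisons that would ordinarily show direction and timing. That stands. But the scope of those comparisons is not stated, and nothing listed yields an adjusted difference with an interval.

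Three stronger readings are tempting and are not supported:

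- *The sample size was computed for a test the plan does not contain.* A reader might infer this because 28 fits a two-sample t-test and no ANOVA effect is that contrast. But the Statistical analysis section lists an independent-samples t-test. It may be meant only for baseline comparisons; the text does not say. No mismatch is established.
- *The false-positive rate is inflated because either F test could reject.* The plan states no such rule, and its Bonferroni correction might cover both tests.
- *The two tests will often contradict each other.* At the plan's only effect size, held constant, they disagree in 1.2% to 4.5% of trials. Larger figures need effects absent from the document: a constant 0.8 SD gives 50% to 58%, and 1.70 fading to 0.85 and then 0 gives 32% to 55%.

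It is also fair to say that replacing group by time with the mean of three as the deciding test is a preference, and that at low correlation adjustment gains little.

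**Conclusion.** The point holds as a free improvement. The plan aims to measure an effect between groups but lists no estimate of that effect adjusted for the pre-test and no interval for it, although the data needed are collected. The size is modest and depends on an unknown correlation: about 0.02 SD off the half-width at rho 0.3, 0.08 SD at 0.5 and 0.20 SD at 0.7, with all 15 per arm analysed. The estimate itself matters more than the narrower interval, because it supplies the direction, units and timing that the listed effect sizes lack.

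The unstated deciding effect and Bonferroni family are mostly missing detail. The 0.75 dilution applies only if the pre-test is a level of time and the group main effect is read as the test of H0-1; the plan says neither.

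**What to change.** For MBI total and, separately, for CSSHP:

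1. Add an ANCOVA estimate of the between-group difference, adjusted for that scale's pre-test score, with 95% CI, at post-test, 1 month and 3 months.
2. State that Bonferroni (or Holm) covers those three comparisons.
3. Keep group by time as the test of change over time. Do not use the time effect, or the group main effect over all four assessments, as evidence on H0-1 or H0-2.
4. Preferably name one deciding contrast: one assessment, or the mean of the three. The mean is stronger for a sustained effect and weaker than group by time for a fading one; a single assessment misses effects at other times.

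The cost is a few ANCOVA runs in the same software on data already planned, plus a few sentences. It needs no new participants or measurements.

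Timing limits what this can do. The document already reports that "alpha coefficients for the pre-test, post-test, first follow-up, and second follow-up assessments were .85, .89, .87, and .88" for the MBI, so the data appear to have been collected. If outcome data have been seen, label the adjusted analysis post hoc and report the planned ANOVA beside it. Naming a contrast now cannot restore prespecified error control, but the adjusted estimates and intervals remain useful.
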